During an initial 2-3 month evaluation period, subjects will complete twice-daily self ratings of mood (including core PMDD symptoms of depression, anxiety, affective lability, irritability) using a 100 mm visual analogue scale (Daily Mood Ratings form-DMR).^{54, 55} Individual items on the DMRs will be measured, scored and plotted using GraphPad Prism (GraphPad Software, Inc. La Jolla, CA) to observe the daily progression of mood symptoms (both in the morning and evening from day to day in the follicular and luteal phase) throughout the evaluation phase and in relation to the woman's menses to ensure proper diagnosis based on DSM-IV criteria. Women also will visit the clinic on a weekly basis where the project coordinator will collect the daily rating forms, and a trained clinician, blind to treatment condition, will interview the subjects using the 24-item Hamilton Rating Scale for Depression (HRSD).⁵⁶ At this time the subjects also will complete a Beck Depression and Anxiety Inventory.^{57, 58} In addition, we will ask them to complete a screening questionnaire on their sleep patterns, to keep daily sleep logs and to adhere to their habitual sleep schedule. This evaluation period will establish the diagnosis of PMDD and will provide information as to when symptoms are likely to occur. It also helps us to design a study schedule based on each patient's individual symptom patterns, and to establish each individual's sleep schedule prior to interventions. As in our previous studies and those of others,⁵⁹ we expect about 5% of patients screened to meet criteria. We especially will recruit women who are non-responsive to other interventions for PMDD, or who seek alternatives to pharmacological or chronic treatments for PMDD.

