9. STATISTICAL CONSIDERATIONS

9.1 General Design Issues

The design is a randomized cross-over contrasting LWT+AM bright light vs. EWT+PM bright light administered in the luteal phase of two separate menstrual cycles, and preceded by 2 evaluation months. To lessen the patient's burden, the 1-night EWT or LWT and the following 7-day BWL interventions will be conducted at home, given at a fixed point in each menstrual cycle, from day 1 to 7 after the mid-cycle LH surge. We anticipate that LWT+7 days of AM BWL (vs. EWT+PM BWL) will produce much greater mood benefits and larger physiological responses, than the one-time light pulses used in our earlier phase-shift studies.

The wake therapy and light interventions proposed in this application are based on our previous studies in PMDD and key published experiments by other investigators that indicate that the combined interventions are efficacious in other mood disorders after one week of treatment and maintained at 9-months follow-up. To provide optimal timing of interventions, we will administer wake therapy in the early-night vs. late-night and light pulses in the AM vs. PM at selected times in relation to sleep (within 30 min of waking and 90 min before sleep onset, respectively).

A crossover treatment design is employed to compare LWT+AM BWL vs. EWT+PM BWL responses within the same individual. As wake interventions lose effectiveness after 1 day, and light treatment effects after 3-4 days, we anticipate minimal carry-over effects of the wake plus light interventions administered a month apart. To further ensure no carry-over effects, there will be a month of no-intervention between the 1st and 2nd treatments. Because our previous studies clearly indicated differences between PMDD and NC subjects occurred primarily in the luteal menstrual cycle phase, we will treat during this menstrual cycle phase rather than in the follicular phase.

Hypothesis (H) 1: For PMDD patients in the luteal phase, LWT+AM BWL, compared with EWT+PM BWL, will A) Decrease scores on SIGH-SAD, BDI, BAI, and DMR, and increase global assessment of treatment effectiveness from baseline to post-intervention; B) Phase-advance urinary melatonin timing measures (acrophase, onset and offset time) in relation to clock time and to sleep measures (onset, end time and mid-sleep times); C) The magnitude of the phase-advance (B, above) will correlate with the magnitude of the symptom changes (A, above) by linear regression.

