9.5 Outcomes

9.5.1 Primary Outcome

- Treatment-Related Mood Rating Changes from Baseline (month 2) to post intervention (months 3,5) :
Mood ratings include Hamilton Rating Scale for Depression (HRSD), Beck Depression Inventory (BDI), atypical depression symptoms as part of the Structured Interview Guide for the Hamilton Depression Rating Scale, Seasonal Affective Disorders version (SIGH-SAD), Beck Anxiety Inventory (BAI), mania ratings, the Psychological General Well-Being Index (PGWI) and daily mood self-ratings (DMR) that include core PMDD symptoms of anxiety and irritability as required during diagnostic evaluation, before, during and after each wake and light intervention at the same time of day (between 15:00-17:00 h). To assess more acute effects on mood that may occur more rapidly during the wake interventions, subjects will complete DMRs twice daily beginning the evening before the wake therapy intervention and continuing until the morning after the recovery night of sleep.
- Treatment-Related Urinary 6-sulfatoxymelatonin (6-SMT) Changes from Baseline (month 2) to post intervention (months 3,5) :
6-SMT is a principal melatonin metabolite that is abundant in urine, well correlated with plasma melatonin, and serves as an excellent marker for circadian phase response.
- Treatment-related changes in objective and subjective sleep measures:
Using actigraphy, we will obtain objective measures of the sleep/wake cycle to ensure appropriate sleep/wake times during wake therapy, and during the light interventions as it is an important biological rhythm with which to compare the intervention-induced melatonin rhythm changes. To assess subjective sleep quality, we will use the Pittsburgh Sleep Quality Index (PSQI) and a visual analogue scale.

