9.6 Data Analyses

Analysis will be performed on data from subjects qualified for participation in accordance to DSM-IV criteria for PMDD (see section 4.3 for criteria and symptoms) as confirmed prospectively by Daily Mood Ratings (DMR).

Mood and Other Ratings: In study month 3 (first treatment), month 4 (washout), month 5 (second treatment) and month 6 (follow-up), we will examine objective (HRSD, atypical, mania – to evaluate symptom severity) and subjective (Beck– to evaluate symptom severity, visual analogue scale-*DMR*) mood (including irritability and anxiety) and physical symptom ratings as a function of diagnosis and time of wake/light interventions.

6-SMT data processing and circadian analyses: From the 6-SMT concentration, urine volume, and the collection times, the 6-SMT excretion rate (ng/h) is computed for each collection interval (the interval between one voiding and the next). Circadian parameters then are computed from analyses of the full time series of 5-min intervals representing each overnight collection. The best-fitting 24-hour cosine curve (for an assumed period of 24 h) is estimated with a least-squares technique to yield the acrophase time (peak), amplitude (1/2 height) and mesor (mean excretion rate (ng/h)) of the fitted curve. To further describe changes in circadian phase and waveform, we use the actual ng/h curve to estimate the circadian timing of nocturnal 6-SMT onsets and offsets algebraically from upward (onset) and downward (offset) crossings of the cosine mesor.

Reproductive Hormones: Levels will be correlated with circadian measures and mood ratings to determine reproductive hormonal influences on circadian physiology and mood.

Daily Sleep Logs will be analyzed for rhythm stability (consistency of standard deviations of sleep onset and offset times from night to night), before vs. after the interventions.

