Actiwatches: Activity and illumination will be examined to determine time-in-bed and any naps that occur during the day. Daily total sleep time, wake time, number of awakenings and distribution of lengths of awakenings for night and day separately in each 24 h period will be determined using the automated sleep-wake scoring algorithm and custom SAS procedures that we have developed.⁷⁰ Extended cosinor analyses⁷⁰ will be done to determine the mesor, amplitude and acrophase of activity and illumination and the f-statistic (with higher values representing more robust and synchronized rhythms that we expect to correlate with improved mood). The mean and maximum light intensities (in lux) and the number of minutes above 1,000 lux

also will be examined. Analyses then will be done comparing activity, sleep and light exposure between groups and time of light intervention with the light and activity summary variables as continuous covariates. Baseline pre-intervention values and post-intervention activity and illumination values also can be compared for a specific light pulse. These analyses will determine if the following variables predict the magnitude of treatment and phase-shift responses: 1) The timing of activity onset and offset, 2) The amplitude of activity at baseline, 3) The illumination levels at baseline.¹ For young adults, the Actiwatch is an accurate method for recording both the in-bed interval and for estimating the time asleep.⁷¹ Although presumably less accurate on a nightly basis than PSG, the Actiwatch is capable of several weeks of round-the clock recording, which would not be feasible with PSG either in the CTRI or at home.

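### Sleep-log rhythm stability is specified only as a before-after comparison, with undefined windows and no LWT+AM BWL versus EWT+PM BWL contrast

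*Combined protocol and SAP*

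**What the plan says.** Section 9.6 gives the sleep logs one sentence. It opens "Daily Sleep Logs will be analyzed for rhythm stability", explains stability as the consistency of standard deviations, and ends with the contrast: "sleep onset and offset times from night to night), before vs. after the interventions". It names no test, model or treatment term, and does not say which nights count as before or after.

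The rest of the plan points to a treatment comparison. Section 9.1 states "The design is a randomized cross-over contrasting LWT+AM bright light vs. EWT+PM bright light", and then "A crossover treatment design is employed to compare LWT+AM BWL vs. EWT+PM BWL responses within the same individual". For actigraphy, 9.6 says "Analyses then will be done comparing activity, sleep and light exposure between groups and time of light intervention". Later in 9.6, PSQI is to be examined for an effect of light intervention.

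Section 9.5.1 has a primary heading "Treatment-related changes in objective and subjective sleep measures", but the instruments under it are actigraphy, PSQI and a visual analogue scale. Sleep-log variability appears in neither 9.5.1 nor 9.5.2.

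Section 4.3 asks women, during the evaluation period, "to keep daily sleep logs and to adhere to their habitual sleep schedule". In Months 2, 3 and 5 there is also an Actiwatch log of subjective sleep times (sections 10.2 and 10.3.3), kept alongside about 10 days of actigraphy starting on the day of the LH surge (LHS; sections 3, 6.2.2 and 6.2.4).

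**The concern.** Women are randomised to the order of two active treatments. Randomisation therefore protects the comparison between the treatment months. It does not protect a comparison of either month with baseline: every woman has her baseline first, and there is no untreated arm. Anything that alters sleep regularity in both treatment months enters a before-after difference in full. Candidates are keeping to a daily light session, repeated logging and monitoring, and regression to the mean.

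At stake is the reading of one measure. As written, the analysis can give a significant change in sleep regularity when the two treatments do not differ and neither caused it, and it gives no estimate of the randomised difference. Because the windows are undefined, the result also depends on a choice of nights made later.

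**Working it through.** **Comparison of the text in 9.6**

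| Measure | Contrast stated |
|---|---|
| Mood ratings | by time of wake/light intervention; treatment-by-time model for hypothesis 1.A |
| Actigraphic sleep | by time of light intervention |
| PSQI | by light intervention |
| Sleep-log SD of onset and offset | before versus after only |

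The treatment-by-time random regression is assigned by name to hypothesis 1.A, which is mood. Hypothesis 1.B uses sleep onset, end and mid-sleep times as references for melatonin timing, not their night-to-night stability. No other section gives sleep-log stability a treatment contrast.

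**Illustration of size**

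The documents state no effect size or power for this measure, so there is no figure to reproduce.

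Inputs from section 9.2: n = 40, two-sided alpha 0.05, correlation 0.45 between assessments. That correlation is stated for sequential assessments; here it is assumed for every pair among baseline, Month 3 and Month 5.

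Assumptions: no difference between treatments, and a shared non-treatment shift d in both treatment months, in units of the SD of one woman's change from baseline.

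*One treatment month against baseline.* Paired t with 39 df, noncentrality d√40.

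*Both treatment months averaged against baseline.* Let each month have variance σ² and correlation ρ.
- Variance of a single change: 2(1−ρ)σ², set to 1.
- Variance of the averaged change: σ²[(1+ρ)/2 + 1 − 2ρ] = 1.5(1−ρ)σ² = 0.75.
- The standardised shift is d/√0.75 = 1.155d, whatever the value of ρ.

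*LWT+AM versus EWT+PM.* The shift cancels, so the expected difference is 0 for every d.

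| d | Noncentrality, one month | Rejects | Noncentrality, pooled | Rejects | Treatment contrast |
|---|---|---|---|---|---|
| 0 | 0 | 5% | 0 | 5% | 5% |
| 0.1 | 0.63 | 9% | 0.73 | 11% | 5% |
| 0.2 | 1.26 | 23% | 1.46 | 30% | 5% |
| 0.3 | 1.90 | 46% | 2.19 | 57% | 5% |
| 0.5 | 3.16 | 87% | 3.65 | 95% | 5% |

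The rates are from the noncentral t distribution. A simulation of 20,000 trials per row agrees within about 1 percentage point.

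**The case against.** The strongest reply is that little depends on this sentence. Sleep-log SD is not itemised in 9.5 and has no hypothesis or power attached. The sleep measures that are itemised through actigraphy and PSQI are compared by intervention. The sentence does not rule out taking before-after changes separately for each intervention and then contrasting them. All of this stands and limits the weight of the point, but none of it supplies the missing contrast or windows.

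Four stronger readings are tempting, and the documents do not support them.

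- *The trial never compares the treatments on sleep, or this is a flaw in a primary outcome.* The actigraphy and PSQI text contradicts the first. The list under the primary sleep heading omits sleep-log SD.
- *The plan will credit any before-after change to treatment.* The sentence says only that the logs will be analysed; attribution would be an inference.
- *The windows are unequal by design*, for example two months of evaluation nights against the few nights after light ends. A sample SD does depend on the number of nights, but no section defines the windows this way, or says how long the daily logs of section 4.3 continue in treatment months. The Actiwatch log and the same LHS-anchored recording exist in Months 2, 3 and 5, so matched windows are available. False-positive rates computed from unequal windows would describe an assumed choice, not the plan.
- *The Actiwatch text repeats the defect.* It says "Baseline pre-intervention values and post-intervention activity and illumination values also can be compared for a specific light pulse", but that is optional, concerns activity and illumination values, and comes after a stated comparison by time of light intervention.

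**Conclusion.** The point holds for one measure. Section 9.6 specifies sleep-log rhythm stability only as before versus after, with undefined windows and without the randomised contrast. A test of that form cannot separate treatment from a change shared by both treatment months.

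The 23% to 87% (one treatment) and 30% to 95% (pooled) rates rest on an assumed shared shift of 0.2 to 0.5 SD, which no document figure supports. They show how the error grows and do not forecast its size here. With no shared shift and matched windows, the before-after test keeps its 5% level. What does not rest on an assumed shift is that the before-after contrast leaves the AM-versus-PM question unanswered for this measure. No listed primary or secondary outcome depends on it.

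**What to change.** In 9.6, replace the before-after phrase in the sleep-log sentence with text to this effect:

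*The night-to-night SD of sleep onset and of sleep offset will be computed over the same LHS-anchored nights in Months 3 and 5, omitting the wake-therapy night, and compared between LWT+AM BWL and EWT+PM BWL within woman, with period in the model. Month 2 values over the matching nights will be shown descriptively. This measure is exploratory.*

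The wake-therapy night should be left out because its sleep times are imposed and differ by treatment: section 5.1 gives sleep at 21:00-01:00 for LWT and 03:00-07:00 for EWT. Including it would put the assigned schedule into the SD. The sentence should also name the nights, and the log they come from, since section 4.3 and section 10.2 describe different logs. The Actiwatch text in 9.6 needs no change.

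The cost is SAP wording only, since the Actiwatch log already covers these months. The small downside is that the sponsor gives up a p-value for the uncontrolled before-after change.

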This design allows us to complete the studies at least two days before the next expected menstrual period. Measuring the circadian profile of urinary melatonin over 2 nights for 30+ h will allow us to assess phase, duration and amplitude changes of melatonin reflective of the underlying circadian pacemaker. In addition, we will assess phase-shift responses of melatonin to light in relation to other critical biological rhythm measures of sleep and activity. To document the sleep/wake cycle and exposure to light intensity and spectra, we will use the Actiwatch device (see description below).

[figure not shown]

Figure 1. Study flow: The luteinizing hormone surge (LHS) documents ovulation, c. menstrual cycle day (CD) 14. Urine samples for 6-sulphatoxy-melatonin (6-SMT) and reproductive hormones (RHs) will be collected for 30+ hours over 2 nights between days 8-9 after the LH surge (c. CD 22-23) in months 2,3,5; actigraphy will begin the day of LHS and continue until day 10 after the LHS (CD 14-24) of months 2,3,5; late wake therapy (LWT) or early wake therapy (EWT) will be administered at home on the night of the LHS; bright morning (AM) or evening (PM) light will be administered on days 1-7 after the LHS (CD 15-21) in a counterbalanced, cross-over design in months 3 and 5. Mood ratings (HRSD+BDI) will be collected as follows: Months 1 & 2 – once per week; Months 3 & 5 – LHS + 0 (Pre-

LWT/EWT), daily LHS +1 → LHS + 2 and once the evening after last treatment (LHS +7/8). Visual Analogue Scales (VAS) for depressed mood, anxiety, affective lability, irritability (Daily Mood Ratings)(core PMDD symptoms) collected daily during Months 1 & 2, and twice daily on LHS + 0 through LHS + 2 (for wake therapy effects) and daily LHS + 3 through LH + 10 (for light treatment effects) in Months 3 & 5. HRSD will be collected once during Month 4 and a once a month after Intervention 2 to monitor relapse.

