Actigraphy Measures: Measures of activity and illumination using the Actiwatch Spectrum device will be obtained for 10 days in the luteal phase starting on the day of the LH surge during the 2nd month of screening evaluation and during each subsequent intervention month. The Actiwatch Spectrum, developed by Respirationics®, a subsidiary of Royal Philips Electronics, is a small device (48.5 x 36.7 x 13.8 mm and weighing 29.8 g with band) containing a piezoelectric linear accelerometer (sensitive to 0.003 g and above), log-linear photometric transducer (sensitive from <0.01 lux to >100,000 lux), 3 photon flux and irradiance color sensors in the red, green, and blue bands of visible light, a microprocessor with 2 Mbits RAM memory that allows for 36 days continuous recording of 1-minute epochs, and associated circuitry. The orientation and sensitivity of the accelerometer are optimized for highly effective sleep-wake inference from wrist activity. The illumination measurements are roughly log-linear from a range below moonlight to the brightest summer day at noon. An important innovative feature of this device is an off-the-wrist sensor, which distinguishes when the participant has removed the device for any reason. The Actiwatch Spectrum also allows us to determine spectral composition of light, which may differentially affect phase-shift, and therefore, treatment responses.⁴⁵

Sleep Interventions: Adherence to appropriate sleep and wake times during the EWT and LWT interventions will be documented by actigraphy. Compliance with wake therapy also will be monitored by having patients leave a message on an answering machine once every half-hour while awake. As they are only awake for 4 hours during wake therapy, they will make 8 calls.

Light Interventions: Subjects will sit in front of a portable (5.5" x 6.25") Litebook® Model 1.2 light box (an array of 60 cool white light-emitting diodes behind a clear

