General Approach to Data Handling and Statistical Analyses: Care will be taken to insure the confidentiality, complete recording, and accurate computerization of the data. Items will be subject to range and relational checks. Crosscheck programs will be used to provide a 100% check of data entry. Descriptive statistics will be calculated on all data items. Distributions, means, medians, standard deviations, ranges, skewness and kurtosis will be calculated for all measurements. Missing data values will be minimized by intensive training of the interviewers in techniques of clarifying answers and checking questionnaires while participants are on-site. When missing values are identified, several approaches such as rescheduling tests or interviews will be used to acquire the necessary data. Furthermore, missing data will be examined to assess randomness. We expect missing data to be randomly distributed and will impute appropriate values. Missing data (i.e. loss to follow-up) will be tested to determine if it is informative, and the methods developed by Diggle⁷² and Ridout⁷³ to test for completely random dropouts will be applied. All available data will be used in our data analysis without any need to estimate missing data (see below).

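### The cosinor F-statistic used as the index of rhythm robustness grows with the number of epochs analysed, so unequal valid recording length would be mixed with rhythm strength

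*Combined protocol and SAP*

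**What the plan says.** The Actiwatch paragraph of section 9.6 plans extended cosinor analyses, which "will be done to determine the mesor, amplitude and acrophase of activity and illumination". From the same fit it takes "the f-statistic (with higher values representing more robust and synchronized rhythms that we expect to correlate with improved mood"). It names no fit index that is free of record length, such as R².

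On recording length, section 3 (Actigraphy Measures) says the data "will be obtained for 10 days in the luteal phase starting on the day of the LH surge", in the second evaluation month and in each intervention month. Sections 6.2.2 and 6.2.4 also give 10 days. The Figure 1 legend words the window as "actigraphy will begin the day of LHS and continue until day 10 after the LHS (CD 14-24) of months 2,3,5".

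On gaps, section 3 says the device has "an off-the-wrist sensor, which distinguishes when the participant has removed the device for any reason". The plan does not say what happens to flagged epochs before the cosinor is fitted. Section 5.4 sets adherence thresholds for wake therapy and for light, but none for wearing the Actiwatch. Section 10.3.3 has recordings checked against logs, with no rule for a valid day. The general data-handling paragraph of 9.6 says both that missing values will be imputed and that "All available data will be used in our data analysis without any need to estimate missing data". Nowhere is a common record length set, or F scaled for the number of epochs.

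**The concern.** F compares explained with residual variation after dividing each by its degrees of freedom. The residual degrees of freedom count the epochs, so F measures strength of evidence for a rhythm, not strength of the rhythm. A longer recording of the same rhythm gives a larger F.

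The plan reads a higher F as a more synchronized rhythm and expects it to go with better mood. If valid recording length varies for reasons unrelated to mood, the variation adds noise and weakens a real correlation. If it varies with mood or with adherence, it can produce a correlation that would be reported as circadian. With no adjustment for record length, the planned analysis cannot separate these cases from a true association.

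**Working it through.** The plan gives no F value, R² or variance for this measure, so there is no figure of its own to reproduce.

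**Inputs**
- From the documents: F as the index (9.6); a nominal 10 days of recording in Months 2, 3 and 5 (section 3).
- Assumed: 1-minute epochs (section 3 gives them only as device capacity, "memory that allows for 36 days continuous recording of 1-minute epochs"); p = 5 fitted parameters for the extended cosinor; R² = 0.30; the numbers of valid days.

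**Step 1: the identity.** F = [R²/(p − 1)] / [(1 − R²)/(n − p)], with n the number of epochs. At fixed R² and p, F is proportional to n − p.

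**Step 2: numbers.** At 10 days n = 10 × 1,440 = 14,400, so F = (0.30/4) / (0.70/14,395) = 1,542. Other lengths, same rhythm:

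| Valid days | n | F | Ratio to 10 days |
|---|---|---|---|
| 5 | 7,200 | 771 | 0.50 |
| 7 | 10,080 | 1,080 | 0.70 |
| 8 | 11,520 | 1,234 | 0.80 |
| 9 | 12,960 | 1,388 | 0.90 |
| 10 | 14,400 | 1,542 | 1.00 |

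The ratio is (n − p)/(14,400 − p), so it does not depend on R². With n in the thousands it barely depends on p.

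**Step 3: the same effect on the R² scale.** F at 7 days equals that of a 10-day recording with odds R²/(1 − R²) = (0.30/0.70) × 0.7 = 0.30. That is R² = 0.30/1.30 = 0.23. At 9 days the odds are 0.386 and R² is 0.278.

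**Step 4: autocorrelation.** Activity counts are serially correlated, so the identity was checked by simulation: a fixed 24-hour cosine, a 3-parameter cosine fit, 1-minute epochs, 200 series per setting.

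| Noise | Mean F, 5 days | 7 days | 10 days |
|---|---|---|---|
| Independent | 1,253 | 1,756 | 2,497 |
| AR(1), 0.90 | 1,271 | 1,781 | 2,532 |
| AR(1), 0.98 | 1,415 | 1,905 | 2,660 |

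With AR(1) noise of 0.90, mean R² is 0.259 at both 5 and 10 days while F doubles.

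**Step 5: how much of the spread in F could be record length.** On the log scale, log F is approximately log odds(R²) + log(days) + constant. If valid days are uniform on 7 to 10, the variance of log(days) is 0.0105; on 9 to 10 it is 0.00092. If the between-woman SD of the log odds of R² is s, independent of wear, the share due to length is V/(V + s²):
- 7 to 10 days: 0.0105/(0.0105 + 0.01) = 51% at s = 0.1; 0.0105/(0.0105 + 0.16) = 6% at s = 0.4.
- 9 to 10 days: 0.00092/(0.00092 + 0.01) = 8% at s = 0.1; under 1% at s = 0.4.

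Both the wear ranges and s are assumptions.

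**Step 6: hours lost within the day.** In the simulation (AR(1) 0.90, 10 days), removal for 1, 2 or 3 hours a day near the activity peak gave:

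| Hours off per day | F, epochs dropped | R² | F, epochs scored zero | R² |
|---|---|---|---|---|
| 0 | 2,532 | 0.259 | 2,532 | 0.259 |
| 1 | 2,347 | 0.253 | 950 | 0.116 |
| 2 | 2,143 | 0.244 | 274 | 0.037 |
| 3 | 1,888 | 0.230 | 34 | 0.005 |

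Scoring removal as zero activity does far more damage than dropping it, and to R² as well as to F. Even when the epochs are dropped, R² moves a little.

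**The case against.** The strongest reply is that the plan shows no unequal wear. Recording is meant to be the same length for every woman and month, logs and device recordings are checked, and missing data are to be examined for randomness. The documents do not say that off-wrist epochs are deleted; if they were filled in, n would stay fixed. F is absent from Hypothesis 1, from the outcomes in 9.5, and from the list of actigraphy predictors that 9.6 itself gives. At equal n, F and R² rank women identically. The extended cosinor is cited to an outside source, so its exact computation cannot be seen here.

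Most of this stands, and it limits the size of the point. It does not remove it. Logs and checks do not equalise record length after early removal, lost days or device failure, and the plan has no rule for those cases. Where lengths do differ, F depends on length and R² from the same fit does not.

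Three stronger readings are tempting, and the documents do not support them:
- A reader might take 10 days in one place and LHS to LHS+10 in Figure 1 as a source of unequal lengths. Each wording applies to every woman and to Months 2, 3 and 5 alike, so it creates no difference between women or months.
- A reader might treat deletion of off-wrist time as the stated rule. It is an inference; the plan gives no rule.
- A reader might conclude that women with worse mood wear the device less and that the F–mood correlation is therefore biased. That is possible, but nothing in the documents shows it.

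**Conclusion.** The point holds conditionally and is minor. The dependence of F on the number of epochs is exact at fixed goodness of fit. Its effect in this trial depends on how much valid recording length will differ, which the documents do not give. An assumed loss of 3 days in 10 costs 30% of F, and a loss of 1 day costs 10%. If wear stays within 9 to 10 days and women differ clearly in rhythm strength, the effect is negligible; if wear varies from 7 to 10 days and women differ little, record length could account for about half the spread of log F. The assumptions are 1-minute epochs, five parameters, R² near 0.30 and the wear ranges; the ratios of F hardly depend on the first three. What is at stake is the interpretation of one exploratory actigraphy correlation.

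**What to change.** In the Actiwatch paragraph of 9.6:
- Name R² of the extended cosinor as the robustness index. Alternatively, keep F but compute it on a common number of valid epochs over the same cycle days in Months 2, 3 and 5.
- State that off-wrist epochs are set to missing, not scored as zero activity.
- Report valid wear time by month.

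The cost is a few lines of text. R² comes from the fit already planned, and no new data are needed. One drawback is that R² is less directly comparable with earlier work that reports F, so F can be shown alongside. R² also does not fully correct for wear lost at the same hours each day, which is why wear time should be reported with it.
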